### 1.2 Secondary Aims

- 1.2.1 To determine the incidence of the following side effects in high risk patients receiving high dose methotrexate as a 24 hour infusion: nephrotoxicity, neurotoxicity, mucositis, hepatotoxicity, and myelosuppression.
- 1.2.2 To describe host polymorphisms that may identify risk of methotrexate toxicity or success of this institutional protocol.
- 1.2.3 To describe predictors of successfully achieving an optimum concentration of methotrexate at the end of a 24 hour infusion of HDMTX in patients at high risk of drug toxicity treated with this individualized high dose methotrexate protocol.

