In addition, despite the fact that MTX pharmacokinetics, tumor response and patient toxicities are known to vary greatly and it is known that several germline polymorphisms play a role in this variation, much controversy about the functional consequences of these polymorphisms still exists. Our study, will, by definition, isolate a population of patients with a known increased propensity for certain MTX toxicities. Because the general population minor allele frequency (MAF) is known for many of the polymorphisms known to affect MTX metabolism, this study will provide a unique opportunity to compare rates of certain of these polymorphisms in our study population to that of the general population. This may help elucidate which polymorphisms truly correlate to deficiencies in MTX metabolism. In addition, we may be able to discover which polymorphisms describe a population best suited for individualized MTX dosing.

Though many genetic targets in the folate cycle and intracellular MTX transportation have already been identified, new target genes continue to be discovered. Given that the knowledge base in this field is rapidly expanding, the decision of which polymorphisms to be tested will be determined at the time of analysis, when the study accrual has been met. Common SNPs currently thought to be involved in methotrexate metabolism, pharmacodynamics and toxicity are listed below:

Polymorphism	SNP effect	Approximate MAF (%)	Clinical effect	Reference
MTHFR 677C>T	Reduced activity	15-25	Both increased and decreased risk of myelosuppression reported	37;38
SLC19A1 80G>A	Reduced activity	30-50	Increased hepatotoxicity	39
MTHFR 1298A>C	Reduced activity	15-20	Decreased myelosuppression	40
TYMS 28-bp triple repeat	Increased transcription	40-50	None reported	41

This research does not qualify for an IND as the use of HDMTX is per standard of care treatment of ALL, and the route of administration or dosage level does not significantly increase risk to the patient.

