#### 3.2.2 Diagnosis

Patients with any malignancy who will receive HDMTX given as a 5 g/m2 infusion over 24 hours and a history of ≥1 of the following:

- Documented decreased renal function, as defined as Creatinine greater than 1.5 x baseline or GFR <65ml/min/1.73m^2.
- History of prior nephrotoxicity with HDMTX as evidence by increased creatinine to 1.5 x baseline or need for dialysis or carboxypeptidase
- History of Grade 3 adverse event (AE) related to HDMTX (mucositis, myelosuppression, nephrotoxicity, hepatotoxicity) based on the NIH Common Terminology Criteria for Adverse Events (CTCAE) version 4.0
- Provider concern patient is at risk for MTX toxicity, such as a prior history of treatment with nephrotoxic chemotherapy, history of HDMTX-related neurotoxicity, or antimicrobial/antifungal therapy

Protocol Version 8.0 Date: June 17, 2015

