### 5.3 Demographic information

Age, race, leukemia type, cytogenetics of leukemia, leukemia risk stratification, disease status, protocol treated according to, concomitant medication, reason for enrollment on protocol and type of adverse event with prior HDMTX.

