- 1b) Explore potential changes in incidence of success (achieving an end infusion peripheral blood MTX concentration between 50-80  $\mu$ M) between sequential administrations of HDMTX. The primary endpoint and sample size calculation refer to the first cycle for each patient.
- Aim 2 2a) Calculate the frequency of adverse effects after each infusion. Success rate over multiple cycles within individual patients will be analyzed using generalized estimating equations for binary outcomes. This method will also be applied to the frequency of adverse events and to the assessment of factors associated with outcome. Continuous and ordinal/non-normal adverse effects will be compared via paired t-test or Wilcox sign rank test respectively.
- 2b) Describe the genotype of various methotrexate metabolizing SNPs in each subject. The polymorphisms of subjects in this study will be compared to published minor allele frequencies and when appropriate will be stratified by race/ethnicity. The purpose of this analysis will be to describe trends away from the major allele frequency in patients known to either have experienced or who are at high risk for developing adverse effects to HDMTX.
- 2c) Examine predictors of success of achieving a  $CP_{ss}$  of 50-80  $\mu$ M. Variables in our analysis will include (but not be limited to) age, sex, disease type, race/ethnicity and measure of pre-MTX renal function. An analysis both with and without SNP genotype will be performed secondary to the likelihood that race/SNP correlations will interfere with SNPs being a truly independent variable. We will initially use chi-square test for group variables and t-test for continuous variables. Logistic regression will be used for multivariable analysis to control for confounders and estimation of adjusted odds ratios. P<0.05 will be considered statistically significant.

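### Aim 2b compares all genotyped subjects as one group with published allele frequencies, so patients entered for acquired or suspected risk may dilute a genetic signal; report by entry reason

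*Combined protocol and SAP*

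**What the plan says.** Secondary aim 1.2.2 is "To describe host polymorphisms that may identify risk of methotrexate toxicity or success of this institutional protocol". Section 9.1, Aim 2b, carries most of it: "The polymorphisms of subjects in this study will be compared to published minor allele frequencies", with stratification by race/ethnicity where appropriate. Its purpose is to describe trends "in patients known to either have experienced or who are at high risk for developing adverse effects to HDMTX".

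Section 2.4 gives the reasoning. It states that "Our study, will, by definition, isolate a population of patients with a known increased propensity for certain MTX toxicities", and says of the comparison with general-population frequencies: "This may help elucidate which polymorphisms truly correlate to deficiencies in MTX metabolism".

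Section 3.2.2 requires only one of four entry routes. Two need a documented reaction to HDMTX: prior nephrotoxicity, or a prior Grade 3 adverse event. The other two do not. One is reduced renal function, with no cause specified. The other is "Provider concern patient is at risk for MTX toxicity, such as a prior history of treatment with nephrotoxic chemotherapy", which also lists antimicrobial or antifungal therapy and, as an exception, earlier HDMTX neurotoxicity. Section 2.4 adds that attendings may enrol further patients at their discretion.

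Section 5.3 records "reason for enrollment on protocol and type of adverse event with prior HDMTX". Neither item is used in Aim 2b. Under Section 5.2 the genetic sample is optional.

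**The concern.** Reading a departure from the population frequency as a marker of poor methotrexate handling works best when the group is defined by poor handling. Here some entrants are at risk because of earlier nephrotoxic chemotherapy, kidney disease of another cause, or a concurrent drug. Those are real risks, but they give no reason to expect anything other than population allele frequencies.

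If such patients are averaged with those who reacted to HDMTX, a true departure is pulled towards the published value. The likely error is a false report of no trend for a variant that matters. The final report could not be read correctly without knowing the mix of entry routes.

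The rest of the plan only partly covers this. Aim 2c examines genotype, but against reaching 50-80 µM, not against toxicity. The GEE for adverse events covers factors associated with outcome without naming genotype. So no analysis explicitly links genotype to toxicity within the study.

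**Working it through.** **The plan's own figure.** The only precision figure is in Section 9.3: 50 infusions, 80% success, interval width 0.22. It reproduces as a Wald interval: 0.80 ± 1.96 × √(0.80 × 0.20 / 50) = 0.689 to 0.911, width 0.222. It concerns the primary endpoint and counts infusions. Nothing comparable is given for the genetic comparison, so what follows is an illustration.

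**Inputs.** Published frequency q0 = 0.20, inside the 15-25% that Section 2.4 gives for MTHFR 677C>T. Assumed, because the documents are silent: an allelic odds ratio of 2.0 in toxicity-prone patients; a share f of the cohort that is prone; N = 50 genotyped patients (100 alleles); population frequencies in everyone else.

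**Dilution.** The odds at q0 are 0.20/0.80 = 0.25. Doubled, they are 0.50, so q1 = 0.50/1.50 = 0.333. The pooled frequency is f × q1 + (1 − f) × q0, so the excess over q0 is f × 0.133. Power is for a two-sided 0.05 one-sample normal test on 100 alleles. Aim 2b plans no test; power serves here only as a measure of sensitivity.

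| f | Pooled frequency | Excess (points) | Apparent odds ratio | Power |
|---|---|---|---|---|
| 1.00 | 0.333 | 13.3 | 2.00 | 0.88 |
| 0.75 | 0.300 | 10.0 | 1.71 | 0.68 |
| 0.50 | 0.267 | 6.7 | 1.45 | 0.40 |
| 0.25 | 0.233 | 3.3 | 1.22 | 0.14 |

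**Range.** From f = 1 to f = 0.5 at N = 50, power goes from 0.82 to 0.36 with q0 = 0.15, and from 0.91 to 0.42 with q0 = 0.25. With an odds ratio of 1.5 and q0 = 0.20 it goes from 0.45 to 0.16. With N = 30 and an odds ratio of 2.0 it goes from 0.70 to 0.27.

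**Does a smaller group cancel the gain from splitting?** Write d for the true excess.

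- Pooled signal-to-noise: f × d / √(q0(1 − q0)/(2N)).
- Restricted to the prone group: d / √(q0(1 − q0)/(2Nf)).
- Ratio, restricted to pooled: 1/√f, which is never below 1.

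At f = 0.5 and N = 50, the pooled value is 0.0667/√(0.16/100) = 1.67, and the restricted value is 0.1333/√(0.16/50) = 2.36. The restricted power is Φ[(0.1333 − 1.96 × 0.0566)/√(0.333 × 0.667/50)] = Φ(0.34) ≈ 0.63, against 0.40 pooled. This treats documented toxicity as a perfect marker of the prone group, so it is a best case.

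**How wide are the intervals?** Suppose 30 patients are genotyped and split evenly, giving 30 alleles per group. The 95% half-width at 20% is 1.96 × √(0.16/30) = 14 points for one group. For the difference between groups it is 1.96 × √(2 × 0.16/30) = 20 points. The contrast between groups would not resolve a 13.3-point difference.

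**The case against.** The strongest reply is that the pooling is declared. The purpose clause of Aim 2b names both patients who have had adverse effects and patients at high risk of them. A reader might infer from the Section 2.4 rationale that the plan takes every entrant to have reacted to methotrexate, or to be genetically prone. The documents do not support that: the phrase there is increased propensity for certain toxicities, and Section 2 attributes part of the risk to kidney function and earlier chemotherapy. This part of the reply stands. What is open to question is the inference drawn from the pooled figure.

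Second, the aim is descriptive, with no test, threshold or power, and Section 2.4 says only that the comparison may help. That stands and limits the importance of the point.

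Third, the net direction of error is not settled. A reader might infer that the comparison must be biased towards no difference. Dilution acts that way other things equal, but ancestry mismatch (stratification is only when appropriate) and optional sampling could shift frequencies either way. Nor is enrichment expected for every variant: the Section 2.4 table reports mixed effects for MTHFR 677C>T, less myelosuppression for MTHFR 1298A>C, and none for TYMS. A true depletion would be diluted in the same way.

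Fourth, the entry routes do not divide cleanly. Reduced renal function may itself follow HDMTX, and a documented-toxicity group still mixes kinds of toxicity. So the split removes one source of mixing, not all.

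Finally, genotype is not excluded from the GEE, and Aim 2c covers the part of aim 1.2.2 on success of the algorithm. That is fair, but it leaves the link between genotype and toxicity unstated.

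**Conclusion.** The point holds as one of interpretation in a secondary descriptive aim. Aim 2b treats all genotyped subjects as one group, the entry criteria admit patients without documented HDMTX toxicity, and no split by entry reason is planned although the data for it are collected.

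If those patients carry population allele frequencies, the departure from the published value is multiplied by the prone share of the cohort. That proportionality follows from arithmetic. The percentages and powers shown do not come from the trial: they rest on assumed shares, effect sizes and genotyped numbers.

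The main risk is an unwarranted statement of no trend. It would go too far to say that the genetic aim is invalid, or that the primary success rate or the safety results are affected; neither depends on this comparison.

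**What to change.** In Section 9.1, Aim 2b, report allele frequencies with confidence intervals against published values for:

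- (a) patients with documented prior HDMTX toxicity: the second and third bullets of Section 3.2.2, or prior HDMTX neurotoxicity, whatever other reason for entry also applies;
- (b) patients entered only for acquired or suspected risk;
- all genotyped subjects, as now planned.

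Base the Section 2.4 inference about deficient methotrexate metabolism on group (a). Present (a) against (b) as description only.

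Name genotype among the factors in the adverse-event GEE of Aim 2a, and make the same change in Section 9.3. Aim 1.2.2 then has a within-study link between genotype and toxicity. It would describe toxicity under the adapted dosing, so it complements group (a) and does not replace it.

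The cost is analysis-plan wording. Section 5.3 already collects the reason for enrolment and the type of prior event, and no added patients, samples or clinical procedures are needed. The drawback is smaller groups and wide intervals, about ±14 points with 15 patients in a group, which the report should state.

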#### 4. TREATMENT PLAN

#### 4.1 Overview of Treatment Plan

Our prospective study will enroll patients who will receive HDMTX given as a 5g/m² 24-hour infusion. Enrolled patients will be receiving HDMTX as determined by their primary provider. Patients are eligible to be enrolled at any time point during their treatment course, and may participate during any one or more of their multiple HDMTX administrations.

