#### Analysis:

Aim 1a) Overall change in the incidence of success with the new protocol (achieving end infusion MTX levels  $50-80\mu M$ ) and

- 1b) change in incidence of success at various infusion times during interim maintenance and interim maintenance-like cycles in which patients are administered HDMTX every 2 weeks, as well as
- 1c) Success rate over multiple cycles within individual patients will be analyzed using generalized estimating equations for binary outcomes. This method will also be applied to the frequency of adverse events and to the assessment of factors associated with outcome. Continuous and ordinal/non-normal adverse effects will be compared via paired t-test or wilcox sign rank test respectively.

Aim 2) To examine predictors of success (achieving CPss of 50-80µM) we will initially use chi-square

test for grouped variable and t-test for continuous variables. Logistic regression will be used for multivariable analysis to control for confounders and estimation of adjusted odds ratios. P<.05 will be considered statistically significant.

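### Two conflicting methods are named for predictors of success and Aim 2c states no analysis unit; if infusions are pooled, the simple tests are anti-conservative for patient-level predictors

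*Combined protocol and SAP*

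**What the plan says.** **Simple tests.** Section 9.1, Aim 2c, on predictors of a level in the target range: "We will initially use chi-square test for group variables and t-test for continuous variables". Then: "Logistic regression will be used for multivariable analysis to control for confounders and estimation of adjusted odds ratios". The threshold is "P<0.05 will be considered statistically significant". Section 9.3 repeats the plan under Aim 2, ending "multivariable analysis to control for confounders and estimation of adjusted odds ratios. P<.05 will be considered statistically significant". Neither place mentions a patient cluster term or a robust variance.

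**GEE.** Section 9.1, Aim 2a: "Success rate over multiple cycles within individual patients will be analyzed using generalized estimating equations for binary outcomes". The next sentence, repeated in section 9.3 under Aim 1c, extends it: "This method will also be applied to the frequency of adverse events and to the assessment of factors associated with outcome".

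**Unit.** Section 4.1 lets patients enrol at any point and says they "may participate during any one or more of their multiple HDMTX administrations". It also allows re-enrolment for later infusions and describes a maximum time on study that covers four doses. Section 9.2 stops accrual at 50 infusions in which the algorithm changed the dose, and section 9.3 expresses success as a percentage of infusions. Against that, section 9.1 (Aim 1b) says "The primary endpoint and sample size calculation refer to the first cycle for each patient". No sentence gives the unit for Aim 2c.

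**Predictors.** Aim 2c lists sex, race/ethnicity, disease type, age and a renal-function measure, and plans models with and without SNP genotype.

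**The concern.** A predictor of success is a factor associated with outcome, so the two sets of methods answer one question. They need not agree. GEE allows for correlation between infusions in the same patient; the chi-square test, t-test and ordinary logistic regression take every record as independent.

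Sex, race/ethnicity, disease type and genotype do not change between a patient's infusions, and age hardly does. If four infusions from one patient enter as four records, that patient's genotype is counted four times, and the standard error is too small wherever the outcomes are positively correlated.

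Two things are at stake. A patient-level factor could be called significant at P<0.05 when nothing is there; section 2.4 hopes to learn which polymorphisms mark patients suited to individualized dosing. And with two methods pre-specified and no order of precedence, the choice could be made after both results are known.

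**Working it through.** **1. The plan's own figure.** Section 9.3 gives 50 infusions, 80% success, and a 95% interval of 69% to 91% (width 0.22). The Wald interval reproduces it: 0.80 ± 1.96 × √(0.80 × 0.20 / 50) = 0.689 to 0.911, width 0.222. This treats the 50 infusions as independent. The plan gives no figure for the predictor analysis.

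**2. Inputs for the predictor tests.** From the plan: 50 infusions, 80% success, alpha 0.05 (taken as two-sided), up to four infusions per patient. Assumed, because the documents do not give them: an intraclass correlation (ICC) of 0.1 to 0.5, and a common number of infusions per patient, m, of 1 to 4.

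**3. Design-effect calculation.** For a predictor constant within patients, the variance is inflated by DEFF = 1 + (m − 1) × ICC. A nominal 5% test that ignores this has true size 2 × [1 − Φ(1.96 / √DEFF)]. Example, m = 4 and ICC = 0.5: DEFF = 1 + 3 × 0.5 = 2.5; 1.96 / √2.5 = 1.24; size = 21.5%; effective sample 50 / 2.5 = 20.

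| m | ICC 0.1 | ICC 0.3 | ICC 0.5 | Effective n |
|---|---|---|---|---|
| 1 | 5.0% | 5.0% | 5.0% | 50 |
| 2 | 6.2% | 8.6% | 11.0% | 45.5 to 33.3 |
| 3 | 7.4% | 12.1% | 16.6% | 41.7 to 25.0 |
| 4 | 8.6% | 15.5% | 21.5% | 38.5 to 20.0 |

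**4. Simulation check of the simple tests.** Beta-binomial outcomes, 80% success, no true effect, a patient-level binary predictor (chi-square without continuity correction) or a patient-level continuous predictor (t-test), 4,000 runs per cell.

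| Setting | Test | ICC 0.1 | ICC 0.3 | ICC 0.5 |
|---|---|---|---|---|
| m = 2, 25 patients | chi-square | 6.8% | 9.8% | 13.1% |
| m = 2, 25 patients | t-test | 5.4% | 9.1% | 11.7% |
| m = 4, 12 patients | chi-square | 9.4% | 17.4% | 25.1% |
| m = 4, 12 patients | t-test | 9.1% | 15.1% | 21.3% |

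With one infusion per patient, the chi-square test gave 4.8% and the t-test 5.0%.

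**5. Ordinary logistic regression against exchangeable GEE.** 500 runs per cell, same binary predictor. Runs that could not be fitted, or in which one group had all successes or none, were dropped, leaving 440 to 494.

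| Setting | Method | ICC 0.1 | ICC 0.3 | ICC 0.5 |
|---|---|---|---|---|
| m = 2, 25 patients | logistic | 3.0% | 5.3% | 8.5% |
| m = 2, 25 patients | GEE | 2.6% | 3.6% | 4.8% |
| m = 4, 12 patients | logistic | 4.8% | 11.5% | 15.5% |
| m = 4, 12 patients | GEE | 5.2% | 8.5% | 6.6% |

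The simulation error at a true 5% is about √(0.05 × 0.95 / 500) = 1 percentage point. Logistic regression shows no clear inflation at ICC 0.1, or at ICC 0.3 with m = 2; it does at m = 4 with ICC 0.3 or more. GEE with 12 patients reaches 8.5% in one cell, so its usual variance is not fully reliable with so few clusters.

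**The case against.** The strongest reply is that the plan may never pool infusions in Aim 2c. The first-cycle sentence sits in the same section. If it governs, each patient gives one record, the simple tests are valid, and GEE is kept for analysis over several cycles. The word initially also suggests only a first look, and a logistic model fitted by GEE would itself yield adjusted odds ratios. On this view only a sentence on unit and precedence is missing.

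Much of this stands. A reader might infer that the plan runs its simple tests on repeated infusions and ignores within-patient correlation. The documents support neither: the unit for Aim 2c is unstated, and GEE is named in both sections. But the first-cycle sentence is limited to the primary endpoint and sample size, and the infusion counts in sections 9.2 and 9.3 point the other way. The joint reading has to be supplied by the analyst.

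The size is also open to challenge. Nothing in the documents supports an ICC as high as 0.5, and section 2.1 notes that levels vary within a patient between administrations. Four infusions each, giving about 50 / 4 = 12.5 patients, is an extreme. Because section 9.2 counts only dose-adjusted infusions, the total analysed could be larger. As an illustration, applying the 58% adjustment rate that section 2.4 reports for patients in a prior study gives 50 / 0.58 ≈ 86 infusions, or about 22 patients at four each. More patients would help GEE, but the size formula depends on m and ICC, not on the total.

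Finally, section 1.2 makes this a secondary, descriptive aim.

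**Conclusion.** The conflict is on the page in both 9.1 and 9.3: two methods for one question, no rule of precedence, and no stated unit for Aim 2c. The consequence is conditional. If infusions are pooled, a nominal 5% test of a patient-level predictor has true size of about 6% to 11% at two infusions per patient and about 9% to 22% at four, under assumed ICCs of 0.1 to 0.5. With one infusion per patient it stays at 5%. The simulated chi-square and t-test broadly agree with the formula; ordinary logistic regression is affected mainly at the higher ICCs.

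It would be wrong to say that false findings are bound to be far more frequent than 5%: that fits only the corner with many infusions per patient and high ICC. The figures do not carry over to factors that vary between infusions, where the error can be smaller or reversed. The per-subject comparison of allele frequencies (Aim 2b) and the primary estimate are not affected. The point should be corrected, but it does not threaten the main result.

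**What to change.** In Aim 2c (section 9.1) and Aim 2 (section 9.3), state the unit of analysis and name one governing method. The simplest change is to make the GEE already in the plan the method for both single-predictor and multivariable analyses of all infusions: logit link, patient as cluster, exchangeable working correlation, and a small-sample variance correction because there may be few patients. Then delete the chi-square, t-test and ordinary logistic sentences, or restrict them explicitly to each patient's first infusion.

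No new data are needed. Compared with the independence analysis, intervals for patient-level predictors widen by √DEFF: from √1.1 = 1.05 to √1.5 = 1.22 times at two infusions per patient, and from √1.3 = 1.14 to √2.5 = 1.58 times at four. Analyses restricted to first infusions would use one record per patient, for example 25 records rather than 50 at two infusions each.
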